9.3.2 Analysis of Secondary Endpoints

The secondary endpoints are:

- Safety parameters including vital signs, laboratory tests, and spontaneously reported AEs and SAEs.
- Proportion of patients who achieve an overall response 8 weeks (Day 56) and 12 weeks (Day 84) after initiation of ECP treatment.
- Duration of response, defined as the length of time a patient maintains a response through Week 16 of the Follow-up Period on a per-patient basis.
- Proportion of patients who achieve an overall response after 4 weeks (Day 28), 8 weeks (Day 56) and 12 weeks (Day 84) of ECP treatment according to the modified Glucksberg criteria
 - Source data will be collected for each patient and entered into the eCRF, and a scoring algorithm will be applied to calculate the grade of aGvHD using the modified Glucksberg criteria.
- Cumulative dose of daily steroids administered from diagnosis of aGvHD to 12 weeks (Day 84) after initiation of ECP treatment.
- Organ-specific grade at 4 weeks (Day 28), 8 weeks (Day 56) and 12 weeks (Day 84) after initiation of ECP treatment.

Overall response (CR+PR) rate at 8 weeks (Day 56) and response determined by the Glucksberg criteria will be summarized by frequency tabulation and analyzed using exact Binomial test and confidence interval. Supportive analysis of response rates over time will be achieved by means of generalized linear mixed effects modelling. Daily steroid dose will be analyzed using mixed model repeated measures analysis. Duration of response will be summarized by Kaplan-Meier curve; the median duration of response and 95% confidence interval will be presented.

9.3.3 Analysis of Exploratory Endpoints

Exploratory endpoints include:

- █ [REDACTED]
- █ [REDACTED]
- █ [REDACTED]
- █ [REDACTED]
- █ [REDACTED]

9.4 SAFETY PARAMETERS

Safety parameters for each patient include vital signs, laboratory tests, and spontaneously reported AEs and SAEs. Adverse events will be graded according to the Common Terminology Criteria for Adverse Events (CTCAE), version 4.0 and will be coded using MedDRA based on the verbatim term collected in the eCRF. Adverse event data will be summarized by system organ classification and preferred term. Vital signs and laboratory values will be summarized by visit and numbers of patients with excursions outside the normal reference range summarized.

10. ETHICAL, LEGAL, AND ADMINISTRATIVE ASPECTS

10.1 DATA QUALITY ASSURANCE

The Sponsor or Sponsor designee will conduct a site visit to verify the qualifications of each Principal Investigator, inspect the site facilities, and inform the Principal Investigator of the responsibilities and procedures for ensuring adequate and correct documentation.

The Principal Investigator is required to maintain adequate and accurate medical records which include all data collected for each study participant. All information recorded on the eCRFs for this study must be verifiable against original source documentation (i.e., medical records). Sponsor or designee Quality Assurance representatives may visit study sites to review data produced during the course of the study, and to assess compliance with applicable regulations pertaining to the conduct of clinical studies.

10.2 CASE REPORT FORMS AND SOURCE DOCUMENTATION

All data obtained during this study should be captured in the Electronic Data Capture (EDC) system promptly. All source documents from which EDC system entries are derived should be placed in the patients' medical records. Measurements for which source documents are usually available include laboratory assessments.

The original EDC system entries for each patient during the 12-week period may be checked against source documents at the study site by the designated site monitor. After review by the site monitor, completed EDC system entries will be uploaded for processing. Instances of missing or uninterpretable data will be discussed with the Principal Investigator for resolution.

The specific procedures to be used for data entry and query resolution using the EDC system will be provided to study sites in a training manual. In addition, site personnel will receive training on the EDC system.

10.2.1 Data Collection

Access to the eCRFs will be carefully controlled and configured according to each individual's role throughout the study. In general, only the Principal Investigator and authorized staff will be able to enter data and make corrections in the eCRFs.

The eCRF should be completed for each patient included in the study and should reflect the latest observations on the patients participating in the study. Therefore, the eCRFs are to be completed as soon as possible during or immediately after the patient's visit or assessment. The Principal Investigator must verify that all data entries in the eCRF are accurate and correct. If some assessments cannot be done, or if certain information is unavailable, not applicable, or unknown, the Principal Investigator should indicate this in the eCRF. Manual checks will identify any clinical data discrepancies for resolution. Corresponding queries will be loaded into the system and the site will be informed about new issues to be resolved on-line. All discrepancies will be solved on-line directly by the Investigator or by authorized staff. Off-line edit checks will be done to examine relationships over time and across panels to facilitate quality data.

After completion, the Principal Investigator will be required to approve the eCRF pages containing the clinical data.

Data about all study drugs dispensed to the patient will be tracked on eCRFs.

10.3 ACCESS TO SOURCE DATA

During the course of the study, a monitor will make site visits to review protocol compliance, compare eCRFs and individual patients' medical records, assess drug accountability, and ensure that the study is being conducted according to pertinent regulatory requirements. Electronic case report form entries will be verified with source documentation. The review of medical records will be performed in a manner to ensure that patient confidentiality is maintained.

Checking of the eCRFs for completeness and clarity, and cross-checking with source documents, will be required to monitor the progress of the study. Moreover, regulatory authorities of certain countries, Institutional Review Boards (IRBs), Independent Ethics Committees (IECs), and/or the Sponsor's Clinical Quality Assurance Group or designee may wish to carry out such source data checks and/or on-site audit inspections. Direct access to source data will be required for these inspections and audits; they will be carried out giving due consideration to data protection and medical confidentiality. The Principal Investigator assures the Sponsor and designee of the necessary support at all times. Local/country specific data protection law is applicable and will be followed.

10.4 DATA PROCESSING

All data will be entered by site personnel into the eCRFs.

The Data Cleaning Specification, to be developed during the initiation phase of the study, will include specifications for consistency and plausibility checks on data, and also include rules for data handling (e.g., what fields are entered for Screen Failures).

Previous and concomitant medications will be coded using the World Health Organization (WHO) Drug Reference List (DRL), which employs the Anatomical Therapeutic Chemical (ATC) classification system. Medical history/current medical conditions and AEs will be coded using MedDRA terminology.

The versions of the coding dictionaries can be obtained or provided by Therakos, Inc.

10.5 ARCHIVING STUDY RECORDS

According to ICH guidelines, essential documents should be retained for a minimum of 2 years after the last approval of a marketing application in an ICH region, and until there are no pending or contemplated marketing applications in an ICH region, or until at least 2 years have elapsed since the formal discontinuation of clinical development of the investigational product. However, these documents should be retained for a longer period if deemed necessary by other applicable regulatory requirements.

10.6 GOOD CLINICAL PRACTICE

The procedures set out in this study protocol are designed to ensure that the Sponsor and Principal Investigator abide by the principles of the GCP guidelines of the ICH and the [Declaration of Helsinki \(1996\)](#). The study also will be carried out in compliance with local legal requirements.

10.7 INFORMED CONSENT/ASSENT

Before each patient is admitted to the study, informed consent/assent will be obtained from the patient (or his/her parent, legal guardian or legally authorized representative) according to the regulatory and legal requirements of the participating country. The ICF must be dated and retained by the Principal Investigator as part of the study records. The Principal Investigator will not undertake any investigation specifically required only for the clinical study until valid consent/assent has been obtained. The terms of the consent/assent and when it was obtained must also be documented in the eCRF.

If a protocol amendment is required, the ICF may need to be revised to reflect the changes to the protocol. If the ICF is revised, it must be reviewed and approved by the appropriate IRB and Ethics Committee and signed by all patients subsequently enrolled in the study as well as those currently enrolled in the study.

10.8 PROTOCOL APPROVAL AND AMENDMENT

Before the start of the study, the study protocol and/or other relevant documents will be approved by the IRBs, Ethics Committees and Competent Authorities (if applicable) in accordance with local legal requirements. The Sponsor must ensure that all ethical and legal requirements have been met before the first patient is enrolled in the study.

The protocol and IRB approval will be submitted to the Investigational New Drug (IND) application for the product to the U.S. Food and Drug Administration for notification/comment.

This protocol is to be followed exactly. To alter the protocol, amendments must be written, approval must be received from the appropriate personnel, and approval must be received from the IRB or Ethics Committees before implementation (if appropriate per regulatory requirements). Following approval, the protocol amendment(s) will also be submitted to the IND under which the study is being conducted and to Competent Authorities (if appropriate per regulatory requirements).

Administrative changes may be made without the need for a formal amendment. All amendments will be distributed to all protocol recipients, with appropriate instructions.

10.9 DURATION OF THE STUDY

For an individual patient, the maximum duration of treatment will be up to 12 weeks, not including the Week 26 Overall Survival assessment. The study is expected to last approximately 3 years.

10.10 PREMATURE TERMINATION OF THE STUDY

If the Principal Investigator, the Sponsor, or the Medical Monitor becomes aware of conditions or events that suggest a possible hazard to patients should the study continue, the study may be terminated after appropriate consultation among the relevant parties. The study may also be terminated early at the Sponsor's discretion in the absence of such findings.

Conditions that may warrant termination include, but are not limited to:

- Discovery of an unexpected, significant, or unacceptable risk to patients enrolled in the study.

- Failure to enroll patients at an acceptable rate.
- Recommendation of the DSMB.

10.11 CONFIDENTIALITY

All study findings and documents will be regarded as confidential. The Principal Investigator and members of his/her research team must not disclose such information without prior written approval from the Sponsor.

The anonymity of participating patients must be maintained. Patients will be identified on eCRFs and other documents submitted to [REDACTED] by their patient number, initials, and/or birth date—NOT by patient name. Documents not to be submitted to [REDACTED] that identify the patient (e.g., the signed ICF) must be maintained in confidence by the principal Investigator.

10.12 OTHER ETHICAL AND REGULATORY ISSUES

If a significant safety issue is identified, either from an individual case report or from a review of aggregate data, then the Sponsor will issue prompt notification to all parties—regulatory authorities, Principal Investigators, IRBs, Ethics Committees and Competent Authorities (if applicable).

A significant safety issue is one that has a significant effect on the course of the clinical trial or program (including the potential for suspension of the trial program or amendments to protocols) or warrants immediate update of informed consent/assent.

10.13 LIABILITY AND INSURANCE

It is assumed that the Principal Investigators have reasonable third-party liability insurance coverage in accordance with all local legal requirements. The civil liability of the Principal Investigator, the persons instructed by him/her, and the hospital, practice, or institution at which they are employed, with respect to financial loss due to personal injury and other damage that may arise as a result of the carrying out of this study, are governed by the applicable law.

10.14 PUBLICATION POLICY

As this is a Therakos, Inc.-sponsored study, Therakos, Inc. will be responsible for publication of study results. The results of this study may be published in a medical publication or journal or may be used for teaching purposes. Additionally, this study and its results may be submitted for inclusion in all appropriate health authority registries as well as for publication on health authority study registry Web sites as required by local health authority regulations.

12. APPENDICES

12.1 APPENDIX A: MODIFIED IBMTR SEVERITY INDEX

Table 4. Criteria for Modified IBMTR Severity Index for aGvHD

Index ^a	Skin Involvement		Liver Involvement			GI Involvement			Upper GI Involvement			
	Stage	Extent of Rash	Stage	Total Bilirubin (mg/dL)	Stage	Volume of Diarrhea (stool output/day)		Stage	Clinical Features			
						Patients < 50 kg	Patients ≥ 50 kg					
A	1	< 25%	0	< 2 (< 34 μmol/L)	0	< 10 mL/kg/d	< 500 mL/d	0				
B ^b	2	25-50%	or	1-2	2-6 (34-102 μmol/L)	or	1-2	10-30 mL/kg/d	500-1500 mL/d	or	1	Nausea, vomiting, anorexia, epigastric pain or burning, and/or food intolerance with a positive upper GI biopsy
C	3	> 50%	or	3	6-15 (103-255 μmol/L)	or	3	> 30 mL/kg/d	> 1500 mL/d	–		
D	4	Bullae	or	4	> 15 (> 255 μmol/L)	or	4	Severe abdominal pain with or without ileus		–		

^a Assign Index based on maximum involvement in an individual organ.

^b Grade B aGvHD includes patients with stage 2 skin and no visceral aGvHD, or stage 0-2 skin and stage 1-2 visceral aGvHD.

12.2 APPENDIX B: MODIFIED GLUCKSBERG CRITERIA**Table 5. Modified Glucksberg Criteria for aGvHD**

Stage	Skin	Liver (bilirubin mg/dL)	Gut (stool output/day)	
			Patients < 50 kg	Patients ≥ 50 kg
0	No GvHD rash	< 2.0	< 10 mL/kg/day	< 500 mL/day or persistent nausea
1	Maculopapular rash < 25% BSA	2.0-3.0	< 10-19.9 mL/kg/day or persistent nausea, vomiting or anorexia, with a positive upper GI biopsy	500-999 mL/day or persistent nausea, vomiting or anorexia, with a positive upper GI biopsy
2	Maculopapular rash 25%-50% BSA	3.1-6.0	20-30 mL/kg/day	1000-1500 mL/day
3	Maculopapular rash > 50% BSA	6.1-15.0	> 30 mL/kg/day	> 1500 mL/day
4	Generalized erythroderma plus bullous formation	> 15.0	Severe abdominal pain with or without ileus	

Grade	Skin	Liver	Gut
I	Stages 1-2	None	None
II	Stage 3 or	Stage 1 or	Stage 1
III	—	Stages 2-3 or	Stage 2-4
IV	Stage 4 or	Stage 4	—

BSA, body surface area; GI, gastrointestinal; GvHD, graft-versus-host disease.

Pages 71-93 Redacted

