3.2.3 Exploratory Endpoints

3.3 CRITERIA FOR DEFINING RESPONSE

The criteria for defining response are as follows:

- Overall response: CR + PR
 - CR: complete resolution of all signs and symptoms of aGvHD in all evaluable organs without addition of next-line systemic treatment.
 - PR: improvement of 1 stage in 1 or more aGvHD target organs without progression in others and without addition of next-line systemic treatment (see [Section 3.1](#) for information regarding next-line treatment).
- No response: Mixed Response or Stable Disease or Progression
 - Mixed Response: at least 1 stage improvement of at least 1 organ, with at least 1 stage worsening in at least 1 other organ.
 - Stable Disease: no significant change in any organ system.
 - Progression: worsening in 1 or more organs by 1 or more stage without improvement in any involved organ.
- Very good partial response (VGPR) [[Martin et al., 2009](#)]:
 - Skin: no rash, or residual erythematous rash involving < 25% of the body surface, without bullae (residual faint erythema and hyperpigmentation do not count).

- Liver: total serum bilirubin concentration < 2 mg/dL or < 25% of baseline at enrollment.
- Gut: tolerating food or enteral feeding, predominantly formed stools, no overt GI bleeding or abdominal discomfort, and no more than occasional nausea or vomiting.

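### Table 5 lists persistent nausea at gut stage 0 for patients of 50 kg or more, against its own stage 1 cell, and has no tie rule, so the secondary Glucksberg response can be mis-scored in either direction

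*Combined protocol and SAP*

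**What the plan says.** Sections 3.2.2 and 9.3.2 make overall response by the modified Glucksberg criteria at Days 28, 56 and 84 a secondary endpoint, analysed with an exact binomial test and confidence interval. Grading is not done by hand: "a scoring algorithm will be applied to calculate the grade of aGvHD using the modified Glucksberg criteria". The criteria are those of Table 5 in Appendix B.

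- **Table 5, 50 kg or more.** Gut stage 0 is "< 500 mL/day or persistent nausea". Gut stage 1 is "500-999 mL/day or persistent nausea, vomiting or anorexia, with a positive upper GI biopsy".
- **Table 5, under 50 kg.** Gut stage 0 is a volume limit only (under 10 mL/kg/day). Gut stage 1 is "< 10-19.9 mL/kg/day or persistent nausea, vomiting or anorexia, with a positive upper GI biopsy".
- **Table 4 (Appendix A, IBMTR).** Upper GI stage 1, with no split by weight, is "Nausea, vomiting, anorexia, epigastric pain or burning, and/or food intolerance with a positive upper GI biopsy". No symptom is listed at stage 0. A footnote adds "Assign Index based on maximum involvement in an individual organ". Table 5 has no such note.

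Section 3.3 turns stages into response. The partial response rule is "PR: improvement of 1 stage in 1 or more aGvHD target organs without progression in others", and the complete response rule is "CR: complete resolution of all signs and symptoms of aGvHD in all evaluable organs".

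**The concern.** An algorithm needs criteria under which each patient falls in one stage, or a rule for choosing when two are met. In the heavier column of Table 5 the same symptom appears at stage 0 without a condition and at stage 1 with a biopsy condition. Because the stage 0 cell joins volume and nausea with an alternative, nausea alone satisfies it whatever the stool output. The absence of a tie rule is a second, independent gap that touches both weight bands.

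One gut stage can decide a partial response. Patients with isolated upper GI disease are eligible with a confirming biopsy (Section 4.1), so the overlap falls on patients the trial expects to enrol. A reported secondary response rate would then rest on a programming choice that the documents do not record.

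**Working it through.** The plan gives no figure to reproduce here. The check is to apply the printed gut rows literally and list every stage that each patient profile meets.

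**Are the columns otherwise consistent?** At 50 kg the volume limits agree: 10 mL/kg × 50 kg = 500 mL and 30 mL/kg × 50 kg = 1500 mL. The stage 1 symptom wording is the same in both columns. The nausea entry at stage 0 is the symptom difference between the columns at stages 0 and 1. (The lighter stage 1 cell is printed with a leading less-than sign; it is read here as 10 to 19.9 mL/kg/day.)

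**Stages met, for patients with persistent nausea:**

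| Weight band | Stool output per day | Biopsy | As printed | Nausea deleted from stage 0 | Highest stage met |
|---|---|---|---|---|---|
| ≥ 50 kg | 100 mL | negative or none | 0 | 0 | 0 |
| ≥ 50 kg | 100 mL | positive | 0, 1 | 0, 1 | 1 |
| ≥ 50 kg | 700 mL | either | 0, 1 | 1 | 1 |
| ≥ 50 kg | 1200 mL | negative or none | 0, 2 | 2 | 2 |
| ≥ 50 kg | 1200 mL | positive | 0, 1, 2 | 1, 2 | 2 |
| < 50 kg | 2 mL/kg | positive | 0, 1 | 0, 1 | 1 |
| < 50 kg | 14 mL/kg | either | 1 | 1 | 1 |
| < 50 kg | 24 mL/kg | positive | 1, 2 | 1, 2 | 2 |

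Two things follow. Nausea meets stage 0 at 500 mL/day or more in the heavier band only. The low-volume, biopsy-positive overlap of stages 0 and 1 exists in both bands, and the deletion alone does not remove it.

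**What this does to response, if the algorithm takes the lowest stage met:**

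1. *Unchanged disease.* Biopsy-positive nausea with low stool output at baseline and at Day 28 scores 0 then 0. There is no one-stage improvement, so no partial response. Taking the highest stage gives 1 then 1, again none.
2. *Missed improvement.* The same patient's nausea resolves. The change should be 1 to 0 but scores 0 to 0, so the gut cannot supply a partial response while another organ remains involved.
3. *False partial response, new nausea.* A patient of 50 kg or more has 700 mL/day without nausea at baseline (stage 1), then 700 mL/day with nausea (stages 0 and 1, scored 0). This counts as a one-stage improvement if nothing else worsens.
4. *False partial response, crossing 50 kg.* At 49.5 kg with nausea and 14 mL/kg/day (14 × 49.5 = 693 mL/day), the stage is 1. At 50.5 kg with nausea and 700 mL/day (700 / 50.5 = 13.9 mL/kg/day), the stages are 0 and 1, scored 0.

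**Size per patient.** With 48 patients, one changed classification moves the rate by 1/48 = 0.0208, or 2.1 percentage points, at each time point where it occurs.

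**The case against.** The strongest reply is that the stage 1 cell carries a biopsy condition, so the stage 0 entry was probably meant for nausea without biopsy confirmation. That may be so, but Table 5 does not say it and the lighter column has no counterpart. The entry is also not needed for that purpose: below 500 mL/day, unconfirmed nausea is already stage 0 by volume. The entry changes anything only at 500 mL/day or more, where it contradicts the volume rows.

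A second reply is that any sensible programmer would take the highest stage met, which resolves every case in the table even without the deletion. This largely stands as a forecast of what would be done. It is not stated for Table 5, and no scoring specification is among the documents.

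Third, the complete response rule demands that all signs and symptoms resolve, so persisting nausea from the disease blocks a complete response whatever the gut stage. That stands; the route to a false response is a partial response.

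A reader might also infer that the problem is confined to heavier patients, or that crossing 50 kg with unchanged low-volume nausea creates a response. Neither holds. The low-volume overlap is the same in both bands, and under either consistent scoring order the stage is the same on both sides of 50 kg.

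**Conclusion.** The inconsistency is real and lies on the face of Table 5: a contradictory stage 0 cell in the heavier column, and no tie rule in either column. The effect on the Glucksberg response at Days 28, 56 and 84 can go either way. Stage 0 at baseline can hide an improvement. A false partial response needs a narrower sequence, such as new nausea, or crossing 50 kg with nausea, in a patient whose stool output is 500 mL/day or more.

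A reader might infer a general inflation of the response rate, or a total of several points from assumed shares of heavier patients with upper GI disease. The documents do not support this. Patients whose nausea is unchanged are not turned into responders, and neither the weight distribution nor the frequency of upper GI disease is given. The firm figure is 2.1 points per affected patient per time point, and it assumes that the algorithm does not already apply a highest-stage rule.

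The primary endpoint uses the IBMTR index in Table 4 and is not affected.

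**What to change.** Reconcile the two cells by removing the nausea alternative from the stage 0 cell of the 50 kg or more column. It is then a volume limit alone and mirrors the column for lighter patients. Add to Table 5 and to the scoring specification that, when criteria for more than one gut stage are met, the highest applies, both at baseline and at every later assessment.

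The deletion makes the wording consistent; the highest-stage rule settles the biopsy-positive overlaps in both weight bands. With both in place, a low-volume, biopsy-positive patient with persistent nausea is stage 1 at any weight.

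The cost is a minor appendix edit and one line in the scoring specification. No additional data, visits or patients are needed.
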